7.1 Safety Analyses for the Aviptadil and Remdesivir Cohorts

The following safety and tolerability outcomes will be analyzed; models will be stratified by disease severity (receipt of invasive mechanical ventilation or ECMO at study entry), as described in section 3 under “stratification”, unless noted otherwise:

- The **primary safety endpoint** is a composite of incident grade 3 or 4 AEs, SAEs, PSESEs, or death through Day 5. The number and proportion of participants experiencing one of these events up through Day 5 will be tabulated, and treatment groups will be compared using a CMH test stratified by disease severity at study entry (2 categories, by receipt of *invasive mechanical ventilation or ECMO* vs. neither). The OR comparing the investigational treatment versus placebo will be estimated with a 95% CI using a logistic regression model that includes the treatment group indicator and the indicator for disease severity at study entry.
 - Mortality will be analyzed as a key secondary outcome, see below.
 - The individual components of the composite outcome will be summarized.
 - Sensitivity analyses for the primary safety outcome: After completion of enrollment, if the Day 5 status for the primary safety outcome is unknown for more than 2% of participants in the mITT cohort, then treatment groups will also be compared for time to event through Day 5 using a log-rank test, stratified by disease severity at study entry; the HR will be estimated with a 95% CI using a stratified Cox proportional hazards model, and the cumulative proportion of participants with events over the first 5 days in each treatment group will be estimated using Kaplan-Meier curves.

Comments:

1. For aviptadil, ***peri-infusion diarrhea is not included in the composite safety outcome*** of incident grade 3 or 4 AEs, SAEs, PSESEs or death unless it is a SAE or leads to discontinuation of the infusion (Appendix H1 of the TESICO protocol). After completion of the infusion, all incident grade 3 or 4 diarrhea AEs are included.
2. Because most participants in the remdesivir cohort will also be randomized to aviptadil versus placebo, we will use the same composite safety outcome for the remdesivir versus placebo comparison as for aviptadil (i.e., diarrhea occurring during and up to 2 hours after the aviptadil/placebo infusion will be excluded as described above).

- All-cause mortality through follow-up will be analyzed using time-to-event methods. Cumulative proportions of participants who died in each treatment group will be estimated using Kaplan-Meier estimates, and summarized in tables (proportion of participants who died by Days 5, 14, 28, 60, 90, month 6) and figures (Kaplan-Meier curves with pointwise 95% CIs). Treatment groups will be compared for time to death using log-rank tests,

stratified by disease severity at study entry, and HRs will be estimated with 95% CIs using stratified Cox proportional hazards models.

- Cause of death will be MedDRA® coded and summarized by treatment group.
- The following composite endpoints will be analyzed using time-to-event methods (cumulative proportions of participants with events will be estimated using Kaplan-Meier curves with pointwise 95% CIs; treatment groups will be compared using log-rank tests; numbers and percent of participants with events will be summarized by treatment group, and overall HRs with 95% CI will be estimated using Cox proportional hazards models):
 - Composite of incident grade 3 or 4 clinical adverse events, SAEs, PSESEs, or death through Day 28
 - Components of the composite endpoint will be also be summarized.
 - In addition to time-to-event analyses, the treatment groups will be compared for the proportion of participants who experienced the composite endpoint by Day 28 using a stratified CMH test, similar to the primary safety analysis on Day 5.
 - Composite of SAEs, PSESEs, or death through Day 28 and Day 90
 - Composite of hospital re-admission or death through Day 90 and Month 6.
- Grade 3 or 4 AEs, SAEs, and UPs will be classified by MedDRA® system organ class. AEs will be graded for severity according to the *DAIDS AE Grading Table*, except for peri-infusion hypotension AEs, which are graded according to Table D-3 in [Appendix D](#).
- Incident **grade 3 and 4 clinical AEs** are reported through Day 28. (A grade 3 or 4 AE is considered “incident” if the event was not present at baseline or increased to grade 3 or 4 from grades 1 or 2, or increased to grade 4 from grade 3.)
 - AEs that were reported to have occurred on Day 0 prior to the first infusion will be considered “baseline” and thus will be excluded from the analysis of incident AEs.
 - Grade 3 and 4 AEs that occur peri-infusion (i.e., during and within 2 hours after the infusion) on Days 0-2 and are reported on the infusion eCRFs will be included as incident grade 3 or 4 AEs, unless noted otherwise.
 - The number and percent of participants with incident grade 3 and 4 AEs will be summarized by MedDRA® system organ class and grade, and by MedDRA® system organ class and grade cut-off (i.e., grade ≥ 3 , grade 4). Comparisons between treatment groups will be for the proportion of participants who experienced AEs of grade 3 or higher through Day 28, using stratified CMH tests or logistic regression, stratified by disease severity at study entry (*invasive mechanical ventilation or ECMO* vs. neither). Treatment groups will be compared for incidence of grade 3 or 4 AEs overall, and by system organ class.
 - System organ classes may be split up into MedDRA® preferred terms (PT) for the most frequent system organ classes, particularly for classes where the treatment difference is significant.
 - Other clinically meaningful AE groupings (beyond system organ class) may be developed by the study team, who are blinded to the treatment effect.
- Grade 1-4 clinical AEs are reported at baseline (Day 0 prior to infusion of the investigational agent), on Days 0-2 peri-infusion (during and within 2 hours after the

infusion), as well as on Days 14 and 28. The peri-infusion AEs are collected as “signs and symptoms” via checklist on the infusion eCRFs.

The analysis of peri-infusion AEs is described in section 6. In particular, the number and percent of participants with peri-infusion AEs will be summarized by day and grade, by type and grade, and by type and action taken (i.e., modification or discontinuation of the infusion).

- Treatment groups will be compared for the proportion of participants who developed **PSESEs** through Day 28 and through Day 90, using stratified CMH tests. In addition to the overall comparison, individual components of the composite PSESE outcome will be tabulated, and compared between treatment groups using stratified CMH tests. The components of the PSESE outcome are listed in [Appendix C](#).

Comment: The composite outcome of *clinical organ failure, serious infections, or death* is identical to the composite of all PSESEs; individual components of clinical organ failure are listed in [Appendix B](#).

Treatment groups will also be compared for the incidence of PSESEs using time-to-event methods; because death is a PSESE, the overall comparison will use Cox proportional hazards models, while comparisons for individual components will use the Fine-Gray model to account for the competing risk of death. Models will be stratified by disease severity at study entry (*invasive mechanical ventilation or ECMO* vs. neither) if event numbers permit.

- Treatment groups will be compared for incidence of a composite of cardiovascular and thromboembolic events, a subset of the organ failure outcome (items b1, e2, e3, and f2 in [Appendix B](#)). Time-to-event methods will be used that take into account the competing risk of death (as described in section 3, using Aalen-Johansen estimates for the cumulative incidence functions, and Gray's and Fine-Gray's methods to compare treatment groups and estimate the sub-hazard ratio).
- **Subgroup analyses:** The impact of study arm on the primary safety outcome (composite of grade 3 or 4 events, SAEs, PSESEs, or death through Day 5) and other important safety outcomes will be assessed for subgroups defined by baseline characteristics, including demographics, duration of symptoms at enrollment, baseline classification of “home”, clinical history and presentation (including disease severity at study entry), use of concomitant medications, and, if available, baseline levels of antibodies, antigen and viral RNA; tests for homogeneity of the treatment effect across subgroups will be carried out. Outcomes and methods for subgroup analyses are described in detail in section 8.5.
- Treatment groups will be compared for mean changes in laboratory test values from baseline to Day 3, and for incidence of grade 3 and 4 laboratory abnormalities at Day 3 (new abnormality or increase in grade). Laboratory tests include the basic metabolic panel (BMP), complete blood count (CBC) with differential, international normalizing ratio (INR), D-dimer, AST, ALT, and bilirubin. Statistical methods are described in section 3. Biomarkers will be log-transformed as needed.
 - For all participants, these biomarkers will be determined locally on Days 0, 1, and 2. Treatment groups will be compared for mean changes from baseline through

Day 2, overall using longitudinal models, and pointwise at Days 1 and 2 using ANCOVA models; models will be adjusted for baseline biomarker levels.

- For participants who are in the ICU on Day 5, these biomarkers are also collected on Day 5. For this cohort, trajectories of mean biomarker values will be described, and treatment groups will be compared for mean changes in biomarker values from baseline through Day 5.
- For renal function lab tests, participants who are on dialysis at study entry will be excluded.

- Pregnancy outcomes will be summarized.

Listings of SAEs, PSESEs, incident grade 3 and 4 AEs, UPs, SUSARs, and deaths (with cause of death) by treatment group will be provided at each DSMB meeting, with new events highlighted. The listings will include important baseline characteristics, such as age, sex, and level of respiratory support at study entry.

Further safety assessments may be considered.

Concomitant medication use is collected at baseline, and daily through Day 7; additionally, any use between Days 8 and 14, and use on Day 28 is reported. Vasopressor use is reported daily for Days 0-14. The following categories of concomitant medications will be summarized by treatment group:

- Corticosteroid use (daily for Days 0-7, any use through Day 14)
- Vasopressor use (daily for Days 0-14)
- Anticoagulation and antiplatelet therapy, by type
- COVID-19 treatments other than corticosteroids, by type
- Other summaries will be provided by request of the DSMB or study leadership.

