Each randomization of investigational agent versus placebo will use a 1:1 allocation, and equal allocation to the four treatment combinations in the 2x2 factorial. Statistical analyses will compare aviptadil versus placebo, pooling participants in strata 1, 2, and 4, and will compare remdesivir versus placebo, pooling participants in strata 1 and 3. To achieve this, it is estimated that 800 participants will have to be enrolled (640 for each pairwise comparison: aviptadil vs. placebo, and remdesivir vs. placebo).

The design assumes that the effects of aviptadil and remdesivir are independent of each other; a possible interaction between the two investigational agents will be assessed in the 2x2 factorial, although power is limited for the interaction test.

Figure 1: Study Design of TESICO. The study includes 4 “design strata”: a 2x2 factorial for aviptadil (VIP) versus placebo and remdesivir versus placebo, and 3 strata with 1:1 randomizations to either investigational agent versus placebo.

Stratum	Percent of Patients
1	60
2	10
3	10
4	20
Sample size for VIP = strata 1, 2 and 4	
Sample size for R = strata 1 and 3	

Population

The study population consists of inpatient adults (≥ 18 years) who have documented SARS-CoV-2 infection within 14 days of enrollment and are receiving high-flow nasal cannula, non-invasive ventilation, invasive mechanical ventilation, or ECMO at enrollment, in whom the current respiratory failure is thought to be due to SARS-CoV-2 infection and in whom respiratory support was initiated within 4 days prior to randomization.

Additional eligibility criteria apply for aviptadil and remdesivir. Participants who have received remdesivir prior to study entry are excluded from randomization to remdesivir.

The **primary endpoint** is a 6-category ordinal outcome that assesses the recovery status of the patient at Day 90, described in [Appendix A](#), and is referred to as “**recovery**”. The categories of the ordinal outcome, from best to worst, start with 3 categories of “recovery” defined by the number of days alive at home and not on new supplemental oxygen, followed by 3 categories for “not recovered” defined as a) discharged but not to home or at home but still requiring continued new supplemental oxygen, b) hospitalized or receiving hospice care, and c) death at day 90.

Primary Objectives

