1.4 Sample Size Estimates

The sample size calculations are aimed at the pairwise comparisons between each of the two investigational agents and its matched placebo. A total sample size of 800 participants is estimated.

To address the first primary objective, participants who are randomized to aviptadil will be compared to those randomized to the matched aviptadil placebo, pooled over design strata 1,

2 and 4. For the second primary objective, participants who are randomized to remdesivir will be compared to those randomized to the matched remdesivir placebo, pooled over design strata 1 and 3. Treatment groups will be compared by intention-to-treat for the 6-category ordinal outcome of recovery on Day 90 (primary outcome) using proportional odds models.

The planned sample size for each pairwise comparison is 640 participants (320 participants in each group, pooled across the corresponding design strata). The sample size is sufficient to detect an odds ratio (OR) of 1.5 with 80% power, using a two-sided test with a significance level of 0.05.

Participants in design stratum 1 (2x2 factorial) will contribute to both comparisons; assuming that 60%, 10%, 10%, and 20% will be enrolled in trial design strata 1-4, respectively, 800 participants in total will result in 640 participants for each of the two pairwise comparisons. The total sample size, which depends on the percentage of participants enrolled in the factorial design, will be periodically assessed by the protocol team.

Sample size calculations are described in detail in Section 6.3 of the protocol.

Blinded sample size re-estimation will be carried out before enrollment is complete to determine whether the planned sample size of 640 participants for each of the pairwise comparisons, followed for 90 days, will be sufficient to adequately power the trial. The blinded sample size re-estimation does not involve unblinding of the treatment difference. It will be based on the pooled outcome data, the relative enrollment into the two disease strata and four design strata, the number of withdrawals prior to the infusion, adherence to the blinded infusions, and the amount of missing data.

2 Interim DSMB Reviews: Goals and Format

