The number and percent of participants with peri-infusion grade 1-4 AEs will be summarized by day and grade, and by type and grade. The percentage of participants with AEs will be compared between treatment groups according to grade cut-offs, e.g., “percent of participants with any AE”, “percent of participants with grade 2 or higher AEs”, etc., using CMH tests. The total number of events and median (IQR) number of events per participant will also be summarized.

Additionally, the incidence of grade 3 and higher AEs will be summarized (number and percent of participants) by MedDRA® System Organ Class and grade using stratified CMH tests. Incidence of grade 3 and 4 AEs will also be compared between treatment groups as part of composite safety endpoints using time-to-event methods.

Significance level, two-sided tests: Unless noted otherwise, statistical tests and confidence intervals will be 2-sided, confidence intervals will have approximate 95% coverage probability, and test results with P-values ≤ 0.05 will be considered “significant”.

Cut-date for interim reviews: Analysis data sets will be locked several days (or weeks) prior to the review date, to allow the unblinded statisticians time to prepare a consistent report.

¹ The Medical Dictionary for Regulatory Activities terminology is the international medical terminology developed under the auspices of the International Conference on Harmonization of Technical Requirements for Registration of Pharmaceuticals for Human Use (ICH). MedDRA® is a registered trademark of the International Federation of Pharmaceutical Manufacturers and Associations (IFPMA)

The cut-date may be earlier than the date of the data lock, to allow for lag time in the reporting of events. Early in the trial, the cut date and lock date will be very close to the review date, to ensure timely safety reviews.

4 Enrollment and Eligibility

For the open report, the following enrollment and eligibility summaries will be provided:

- Enrollment over calendar time: plot by day or week, cumulative and increments.
- Enrollment by study design stratum (4 strata), and pooled across the relevant design strata for the aviptadil/placebo and remdesivir/placebo comparisons.
- Enrollment by site pharmacy and by country: number (%)
- Eligibility: number (%) and reasons for eligibility violations

These summaries will be provided overall, and by disease severity randomization stratum.

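### No committed preferred-term table by arm for grade 3/4 AEs or SAEs in all organ classes; the split is optional and steered partly by class-level significance

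*SAP*

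**What the plan says.** For incident grade 3/4 AEs, SAP section 7.1 compares "the proportion of participants who experienced AEs of grade 3 or higher through Day 28" and sets the level of comparison: "Treatment groups will be compared for incidence of grade 3 or 4 AEs overall, and by system organ class". SAP section 3, in the paragraphs on adverse events, repeats the plan by organ class and grade. SAEs and unanticipated problems are likewise classified in section 7.1 by organ class.

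The step down to preferred terms is worded as something that may be done, "for the most frequent system organ classes, particularly for classes where the treatment difference is significant". Section 3 supplies the meaning of significant: p ≤ 0.05, and "statistical tests and confidence intervals will be 2-sided".

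Other parts of the SAP give event-level output:
- **PSESE components** are each tabulated and compared by stratified CMH test through Day 28 and Day 90, with Fine-Gray comparisons in addition (section 7.1). Appendix C lists 19 items, including death.
- **Peri-infusion AEs** are shown by type and grade, and by type and action taken (sections 6.1 and 6.2).
- **Grade 3/4 laboratory abnormalities** are compared, and **cause of death** is coded and summarised by arm (section 7.1).
- **Listings** of SAEs, incident grade 3/4 AEs and other events go to the DSMB by treatment group (sections 2 and 7.1).

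**The concern.** A system organ class pools many unrelated terms. If a drug raises one term, the background events of critical illness in the same class dilute the difference, and opposite shifts in two terms can cancel. Choosing which classes to open up partly by class-level significance therefore uses a weak signal, and it makes the content of the AE table depend on the results.

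Section 7.2 says that safety data on aviptadil are limited, so an unanticipated specific reaction is one of the things an AE table should make visible. PSESEs are a fixed list of events expected in this population, and the peri-infusion tables stop 2 hours after the infusion. A clinical event outside both, in a class that nobody chooses to split, would appear in DSMB listings. No count by term and arm is promised for it.

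**Working it through.** The SAP gives no AE rates and no detection figure, so there is nothing of its own to reproduce. The calculation below illustrates how far a class-level test reflects a single-term difference.

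**Inputs from the SAP**
- Group size: "The planned sample size for each pairwise comparison is 640 participants (320 participants in each group, pooled across the corresponding design strata" (section 1.4), so n = 320 per arm. Safety analyses are by mITT, so the actual numbers may be somewhat smaller.
- Two-sided 0.05 (section 3).

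**Assumed inputs**
- One preferred term at 1% on placebo and 4% on the agent (variant: 1% and 5%).
- Other terms in the class have a combined background b, equal in both arms and independent of the term.

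**Formulas**
- Class risk = 1 − (1 − b)(1 − term risk).
- Power = Φ[(|p2 − p1| − 1.96·SE0)/SE1], where SE0 = √(2·p̄(1 − p̄)/n), SE1 = √((p1(1 − p1) + p2(1 − p2))/n) and p̄ = (p1 + p2)/2.

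**Term itself, 1% vs 4%.** p̄ = 0.025, SE0 = 0.01234, SE1 = 0.01229. (0.03 − 1.96 × 0.01234)/0.01229 ≈ 0.473, and Φ = 0.68. A simulated Mantel-Haenszel test (unstratified, 200,000 replicates) gives 70%.

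**Class at b = 5%.** Risks are 1 − 0.95 × 0.99 = 5.95% and 1 − 0.95 × 0.96 = 8.80%, a difference of 2.85 points. SE0 = 0.02066, SE1 = 0.02063. (0.0285 − 1.96 × 0.02066)/0.02063 ≈ −0.58, and Φ = 0.28.

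Results for class-level power (formula and simulation agree within about 1.5 percentage points):

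| Class background b | Class risks, term 1% vs 4% | Power, 1% vs 4% | Power, 1% vs 5% |
|---|---|---|---|
| 2% | 2.98% vs 5.92% | 44% | 63–64% |
| 5% | 5.95% vs 8.80% | 28% | 43% |
| 10% | 10.9% vs 13.6% | 18% | 28% |
| 20% | 20.8% vs 23.2% | 11% | 16% |
| Term alone | – | 68–70% | 84–88% |

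**Reading the table against the split rule.** At 20% the dilution is worst, but such a class would plausibly be among the most frequent and so eligible for splitting on frequency alone. At 2% or below the dilution is milder: the formula gives 54% at b = 1% and 60% at b = 0.5% for 1% vs 4%. The exposed region is in between, roughly 5–10% under these assumptions, where a class may not count as most frequent and yet has enough background to mask a single term.

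**The case against.** The strongest reply is that a reader might infer two things which the SAP does not say.

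The first is that preferred terms appear only where the class-level test is significant. In the split sentence, frequency is the criterion and significance only the emphasis. That stands: a frequent class can be split whatever its p-value.

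The second is that a single-term harm would usually be averaged away and left uncounted. That is not supported either. Dilution is greatest in the frequent classes, which are the ones named for splitting. Many serious events of critical illness (infarction, stroke, thromboembolism, bleeding, arrhythmia, renal replacement, hepatic decompensation and others) are tabulated and tested one by one as PSESE components, with no significance filter. The known aviptadil effects have their own peri-infusion tables. Every incident grade 3/4 AE and SAE is listed by arm for the DSMB, which may also ask for further summaries, and AE groupings beyond organ class may be developed by blinded staff.

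All of this narrows the gap without closing it. A listing is not a count with a denominator, and under section 15 the closed report goes only to the DSMB, its Executive Secretary and the unblinded statisticians. The extra groupings are optional. Even the split of frequent classes is optional.

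It is also fair to say that the 70% for the term is the power of a test, while the remedy is a descriptive table. The gain is visibility of the counts, not a new test with that power.

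**Conclusion.** The point holds as a limited reporting gap. The SAP does not commit to a preferred-term table by arm for incident grade 3/4 AEs or SAEs across all organ classes. The split is discretionary, aimed at frequent classes and steered toward those with a significant difference. The uncovered case is a clinical grade 3/4 event that is not a PSESE, arises outside the peri-infusion window and belongs to an unsplit class of middling frequency.

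Under the assumed 1% vs 4% term and 320 per arm, class-level significance would flag the class in 28% of trials at 5% background and 18% at 10%, against about 70% for the term. That shows that class-level significance is a poor guide to which classes to split. It must not be read as the chance that a harm goes unseen: that would need AE rates, knowledge of which classes would be split, and the contribution of the other safety outputs, and the SAP settles none of these. The point affects no efficacy conclusion, sample size or stopping boundary. It is a worthwhile improvement, not a serious flaw.

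**What to change.** In SAP section 7.1, replace the sentence on splitting organ classes with a commitment along these lines: incident grade 3/4 AEs and SAEs will be tabulated by preferred term within system organ class and treatment group, for all classes and regardless of the class-level result, with risk differences and 95% CIs; the table is descriptive.

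AEs are already to be coded in MedDRA (section 3), so no new data are needed, and no existing test changes. The cost is longer tables and more terms that differ by chance, which is why the table should be labelled descriptive and carry no significance filter.
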